### Hathari ya vurugu (Risk of Violence)

Kwa kila maelezo yanayofuata, (28-31) chagua jibu linalo onyesha ni mara ngapi tukio limetokea katika miezi 12 iliyopita

|  | Kamwe | Mara
chache | Wakati
mwingine | Mara
nyingi |
|--|-------|----------------|--------------------|----------------|
| 28. Katika miezi 12 iliyopita, mchumba wako amewahi kuku tukana au kukufanya uhisi vibaya?                   |       |                |                    |                |
| 29. Katika miezi 12 iliyopita, mchumba wako amewahi kukugonga, kukupiga mateke, kukuvuta au kukupiga?        |       |                |                    |                |
| 30. Katika miezi 12 iliyopita, mchumba wako amewahi kumgonga, kumpiga mateke, kumvuta au kumpiga mtoto wako? |       |                |                    |                |
| 31. Katika miezi 12 iliyopita, mchumba wako amewahi kukulazimisha kufanya ngono?                             |       |                |                    |                |

### Ufahamu wa PMTCT

Tafadhali chagua jibu linalofaa:

32. Wakati wa uja uzito, ninapaswa kufanyiwa uchunguzi wa kiwango cha virusi? (Viral load?)
- La, upimaji wa kiwango cha virusi hufanywa tu baada ya kujifungua
  - Kati ya mara moja na mbili
  - Angalau mara tatu
  - Sijui
33. Wakati wa uja uzito, inashauriwa kwamba wanawake walio na maambukizo ya VVU wameze dawa za ART wakati hawajihisi vizuri pekee.....Ukweli/Uwongo
34. Je nimependekezwa kuhudhuria idadi gani ya chini, ya clinic za ANC ?
- 2
  - 3
  - 4
  - 5

### Motisha ya PMTCT na Ufanisi wa Kibinafsi

Tafadhali chagua jibu linaloonyesha kiwango ambacho unakubali au kutokubaliana na kila moja ya sentensi zifuatazo..

|  | Sikubaliani
Kabisa | Sikubaliani | Sina
Maoni | Nakubaliana | Nakubaliana
sana |
|--|-----------------------|-------------|---------------|-------------|---------------------|
| 35. Ninajua naweza kudumisha uzingatiaji kamili wa dawa zangu wakati wote wa uja uzito, hata kukiwa na watu wengine.               |                       |             |               |             |                     |
| 36. Ni muhimu sana kwangu, kujifungua mtoto wangu kwenye kituo cha afya, badala ya nyumbani.                                       |                       |             |               |             |                     |
| 37. Nina wasiwasi kwamba sitaweza kupata usafiri kwenda kwa kituo cha afya wakati wa kujifungua mtoto.                             |                       |             |               |             |                     |
| 38. Shughuli zingine – kama kazi, majukumu ya nyumbani, ulezi wa watoto – zinaweza kunizuia kuhudhuria taratibu zote za ANC/PMTCT. |                       |             |               |             |                     |
| 39. Kuhudhuria taratibu zote ya ANC/PMTCT ni muhimu sana kwangu.   |                       |             |               |             |                     |

|   | Sikubaliani
Kabisa | Sikubaliani | Sina
Maoni | Nakubaliana | Nakubaliana
sana |
|---|-----------------------|-------------|---------------|-------------|---------------------|
| 40. Nilichelewesha kuja kupokea huduma za ANC kwa sababu ya wasiwasi unaohusiana na mfiduo wa COVID-19  |                       |             |               |             |                     |
| 41. Nilichelewesha kutafuta huduma kwa sababu mimi, au mtu katika nyumba yangu alikuwa anajisikia vibaya na sikutaka kuhatarisha wengine kwa sababu ugonjwa |                       |             |               |             |                     |

|  |  |  |  |  |  |
|--|--|--|--|--|--|
| 42. Sitaki kuhudhuria kliniki ya ANC mara kwa mara kwa sababu nina wasiwasi juu ya mfiduo wa COVID-19                        |  |  |  |  |  |
| 43. Nina wasiwasi ya kwamba kujifungua hospitalini kunaweza kutuweka hatarini, mimi na mtoto kuambukizwa na COVID-19         |  |  |  |  |  |
| 44. Kusafiri kwenda na kutoka hospitalini imekuwa ngumu zaidi (gharama na / au upatikanaji wa magari) kwa sababu ya COVID-19 |  |  |  |  |  |

Asante kwa wakati wako na ushiriki.

**Kiambatisho IIB: Utafiti wa wiki ya nne baada ya kujifungua (Kituo chenye, na kisichokua na mfumo)**

***Kujazwa na muuliza maswali***

Nambari ya Utafiti (Study ID): \_\_\_\_\_

Tarehe ya mahojiano \_\_\_\_\_

Majina ya muulizaji maswali kwa kifupi (Interviewer Initials) \_\_\_\_\_

1. Ulifungua mtoto wako wapi?
  - a. Hospitalini/Kituo cha Afya
    - i. Ikiwa ni hivyo, tafadhali eleza ni wapi \_\_\_\_\_
  - b. Kwa mkunga
    - i. Ikiwa ni hivyo, tafadhali eleza eneo ulilo jifungua \_\_\_\_\_
  - c. Nyumbani
  - d. Kwingine
    - i. Tafadhali fafana \_\_\_\_\_
2. Uchungu wa kujifungua ulikuchua takriban muda gani kabla ya ujifungue?
  - a. < masaa 2
  - b. Kati ya masaa 2 – 5
  - c. Kati ya masaa 6 -12
  - d. > Zaidi ya masaa 12
3. Je, wewe au mtoto wako mchanga, mlipatwa na matatizo yoyote?
  - a. Ndio
    - i. Tafadhali elezea tatizo lilolo mkumba mama na/au mtoto kando kando:  
\_\_\_\_\_  
\_\_\_\_\_
  - b. Hapana

**Hali ya Mpenzi, na kujulisha wengine kuhusu hali yako**

4. Je, hali yako ya mahusiano ni?,
  - a. Sijaoa
  - b. Nimeolewa
  - c. Sijaoa lakini niko na uhusiano
  - d. Nimeachana na mchumba/mume (separated)
  - e. Nimepewa talaka (Divorced)
  - f. Mjane
  - g. Ingingine, fafana \_\_\_\_\_
5. Je, hali yako kimaisha ni?
  - a. Sina mpenzi kwa sasa
  - b. Naishi kando na mpenzi
  - c. Naishi pamoja na mpenzi
6. Je, mpenzi wako wa sasa ndiye baba wa mtoto wako mchanga?.....Ndio/Hapana
7. Je, ni nani umemfahamisha kuhusu hali yako ya VVU? Chagua majibu yote yanayofaa...
  - a. Hakuna
  - b. Mpenzi/Mume wangu
  - c. Mmoja au Zaidi katika familia
  - d. Rafiki mmoja, au zaidi
  - e. Mzazi mmoja, au zaidi
8. Je, hali ya virusi ya mchumba wako ikoje?
  - e. Yuko na VVU
  - f. Hana VVU
  - g. Sijui
  - h. Sina mchumba kwa sasa
9. Kwa kawaida, ni nani hufanya uamuzi kuhusu utumizi wa pesa katika boma lako?
  - g. Mchumba wangu, kila wakati

- h. Mchumba wangu zaidi kuniliko
  - i. Sote, kwa usawa
  - j. Mimi, mara nyingi kuliko mpenzi wangu
  - k. Mimi, kila wakati
  - l. Sina mchumba kwa sasa
10. Mapato ya wastani ya kila wiki katika boma lako ni?
- f. Chini ya 500 KES
  - g. 500-750 KES
  - h. 750-1,000 KES
  - i. 1,000-2,500 KES
  - j. Zaidi ya 2,500 KES
11. Nina wasiwasi kwamba sitakuwa na pesa za kutosha kunifikisha hospitalini kwa huduma zangu au za mtoto wangu
- a. Nakubali kabisa
  - b. Nakubali
  - c. Sikubali
  - d. Sikubali kabisa

#### Usaidizi kutoka kwa Mpenzi

12. Ni mara ngapi mchumba wako alikuunga mkon, wakati wa uja uzito, kwa njia zifuatazo,:

|  | Kamwe | Mara chache | Wakati mwingine | Kila Wakati |
|--|-------|-------------|-----------------|-------------|
| 12b. Kukupa pesa za usafiri kwenda hospitalini                               |       |             |                 |             |
| 12c. Kukupa ushauri wa jinsi ya kuishi na afya ukiwa mja mzito               |       |             |                 |             |
| 12d. Kukusaidia na majukumu ya nyumba, ili upate kupumzika                   |       |             |                 |             |
| 12e. Kukusaidia na majukumu ya nyumba ili uweze kuhudhuria taratibu za PMTCT |       |             |                 |             |
| 12f. Kukumbusha kumeza dawa  |       |             |                 |             |
| 12g. Kuku kumbusha umuhimu wa kufuata maagizo ya daktari                     |       |             |                 |             |
| 12h. Kutoa pesa za kununua dawa au vitamini                                  |       |             |                 |             |
| 12i. Mume wangu alinitia moyo mda wote wa ujaizito                           |       |             |                 |             |
| 12j. Mimi na mume wangu tuliomba pamoja kwa usala wa mimba na kujifungua.    |       |             |                 |             |

13. Je, mpenzi wako alihudhuria kliniki yoyote ya PMTCT na wewe?
- a. Hapana, hakuhudhuria yoyote
  - b. Alihudhuria moja
  - c. Alihudhuria mbili
  - d. Alihudhuria tatu au zaidi
  - e. Sina mchumba kwa sasa.
14. Ikiwa ni la kwa (13), ni sababu gani ilimfanya ashindwe kuhudhuria?
- a. Alikuwa kazini wakati wa kliniki zangu za PMTCT \_\_\_\_\_ Ndio / Hapana
  - b. Anaishi au anafanya kazi mbali \_\_\_\_\_ Ndio/Hapana
  - c. Alihisi kutokaribishwa au kuto jihisi huru kliniki \_\_\_\_\_ Ndio/Hapana
  - d. Sikutaka ahudhuria \_\_\_\_\_ Ndio/Hapana
  - e. Hakutaka kuhudhuria \_\_\_\_\_ Ndio/Hapana
  - f. Alikuwa na majukumu mengine \_\_\_\_\_ Ndio/Hapana
15. Je, mpenzi wako aliweza kukupa usaidizi wakati wa kujifungua? Tafadhali chagua jibu lililo sahihi zaidi.
- a. Sina mpenzi wa kwa sasa
  - b. Hapana, mpenzi wangu hakutoa usaidizi wowote kwa wakati wa kujifungua kwangu
  - c. Mpenzi wangu alinipa alinifadhili ili nifike hospitali, lakini hakuja.
  - d. Mpenzi wangu alinindikiza hadi hospitali nilipokuwa na maumivu ya kujifungua
  - e. Mpenzi wangu alinitembelea hospitali baada ya kujifungua.
  - f. Mwenzi wangu wa kiume alinipeleka hospitalini wakati maumivu ya kujifungua yalipoanza, na akanitembelea baada ya kijifungua.

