| Targeted outcomes | 
 
•Efficiency of sample processing
 
•ART initiation for HIV+ infants
 
•Retention through 18m
 
 | 
 
•Appointment attendance
 
•ART adherence
 
•Hospital delivery
 
•Infant linkage to EID by 6wks postnatal
 
 | HITSystem 2.0, plus: 
 
•VL testing through 6m pp
 
•Efficiency of VL testing
 
•Clinical action based on VL results
 
•Male partner support
 
 |

EID= early infant diagnosis; PMTCT= prevention of mother-to-child transmission; VL= viral load; ART = antiretroviral therapy; ANC=antenatal care, pp=postpartum

The screenshot shows a dashboard with five main alert sections:

- Search:** Fields for PMTCT ID, Mother ID, and Delivery Date, with Reset and Search buttons.
- Enrollment Alerts - Lab and Meds:**
  - 0 Enrollment Medications Not Received
  - 3 Lab Results Not Received (2 days past sample)
  - 0 Mom not started on ART (1 week past enrollment)
- Viral Load Alerts:**
  - 14 BaseLine VL Sample Not Collected
  - 0 Repeat VL Sample Not Collected
  - 12 VL Sample Not Received at lab
  - 0 VL Result Not Posted
  - 0 VL > 1000 Copies not reviewed
  - 0 Mother not informed of VL results
- Adherence Alerts:**
  - 19 Missed follow-up appt.
  - 0 Missed ART Collection
  - 2 Adherence < 95%
- Delivery Alerts:**
  - 8 Unknown Delivery Status
  - 0 Infant not enrolled in EID

Figure 1A HITSystem 2.1 web-based provider dashboard displays alerts for patients with delayed services or missing status information.

The screenshot shows the 'Viral Load' tab with the following fields and options:

- VL Sample Collection Date:** 01/11/2018
- Shipped Date:** 02/11/2018
- Received Date:** 06/11/2018
- Level:** Above detectable level
- VL Results:** 2345
- Scheduled Date of Repeat VL Test:** (empty field)
- Result Action Taken:** -Select- (dropdown menu with options: Adherence Counseling, Switch to 2nd line Regimen, Switch to 3rd line Regimen)
- Result Date:** 21/11/2018
- Clinician Acknowledges Results:** Yes
- Result Notification Date:** (empty field)
- Destination Lab:** KEMRI Nairobi
- New Test** button

Figure 1B Viral Load tab of HITSystem 2.1 patient services tracking register. Fields pertain to test performance, test result notification chain, and patient follow-up (repeat test ± clinical action).

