### Objective 1 specific methods:

**Evaluate the efficacy of HITSystem 2.1 to increase the proportion of womens who receive complete PMTCT services through 6 m postpartum, per Kenyan guidelines.**

**Objective 1 outcomes.** The primary outcome for Objective 1 is the proportion receiving "complete PMTCT," an aggregate measure incorporating the documented receipt of all

designated services across the 3 PMTCT phases: maternal ART initiation, antenatal appointment attendance, facility delivery, EID linkage by 7 weeks of age, maternal VL testing and clinical action per national

Table 6. Aim 1 primary outcome: Services required for "complete PMTCT"

| Antenatal  | Delivery                | Postpartum (through 6m)   |
|--|-------------------------|---|
| 

• ART initiation

• On-time appointment attendance

• VL testing per guidelines

• Clinical action upon detectable VL

 | Hospital-based delivery | 

• EID linkage by 7 weeks

• VL testing per guidelines

• Clinical action upon detectable VL

 |

guidelines through 6 months postpartum (Table 6). Participants who receive all indicated services per guidelines will be coded as 1 or 'yes'. Participants missing  $\geq 1$  service will be coded as 0 or incomplete PMTCT services.

**Secondary outcomes** associated with Objective 1 will include gestational week at PMTCT enrollment, duration of PMTCT retention (weeks), and ART adherence (proportion >95%, proportion with missing/late prescription refill). Proportions will be calculated to describe each component of "complete PMTCT" separately (appointment attendance, VL monitoring, hospital delivery, EID linkage). Patient and facility-level factors will be assessed for their moderating impact on complete PMTCT. Provider characteristics will be aggregated and treated as facility-level variables. To assess pathways through which the HITSystem 2.1 works, we will measure provider and patient information and motivation as potential mediators

both pre- and post-intervention, and across study arms. Preterm births and infant weight at birth will be documented. We also will measure the proportion and timing/age of any HIV transmissions to infants, and maternal and/or infant deaths.

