**Statistical analyses for objective 1 (complete retention).** Data from women who have a documented reason for incomplete care at the study hospital (e.g. transfer facility, pregnancy loss, maternal death) will not be included in analyses. To demonstrate the efficacy of HITSytem 2.1 versus SOC, we will test for differences between arms by modeling complete PMTCT as a function of study arm and selected covariates (e.g., age, partner support, depression) using logistic mixed models with a random site intercept (to adjust for clustering). In post hoc analyses we will explore patient and facility-level characteristics as potential moderators of the effect of HITSytem 2.1, and examine changes in key individual level factors (disclosure status, partner status, depression, partner support) at the midpoint (delivery) and again at the end (6m postpartum). To assess mediating factors, we will compute average levels of provider knowledge and motivation for each site at baseline and end of study. These knowledge and motivation scores, as well as patient knowledge and motivation levels, will be compared pre-post intervention and between study arms to assess change within and between sites. In addition, provider and patient knowledge and motivation will be examined as predictors of PMTCT completion using logistic regression.

[figure not shown]

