#### Partner Support

12. How often during your pregnancy did your male partner support you in the following ways:

|  | Never | Rarely | Sometimes | Often |
|--|-------|--------|-----------|-------|
| 12b. Provided money for transport to the hospital?   |       |        |           |       |
| 12c. Gave you advice on remaining healthy while pregnant?                                    |       |        |           |       |
| 12d. Helped you with household responsibilities so that you could rest?                      |       |        |           |       |
| 12e. Helped you with household responsibilities so that you could attend PMTCT appointments? |       |        |           |       |
| 12f. Reminded you to take your medication  |       |        |           |       |
| 12g. Reminded you of the importance of following doctor's instructions.                      |       |        |           |       |
| 12h. Provided money to purchase medication or vitamins?                                      |       |        |           |       |
| 12i. My husband gave me encouragement throughout my pregnancy                                |       |        |           |       |
| 12j. Me and my husband prayed together for a safe pregnancy and delivery                     |       |        |           |       |

13. Did your partner attend any PMTCT appointments with you?
- a. No, he did not attend any
  - b. He attended 1
  - c. He attended 2
  - d. He attended 3 or more.
  - e. N/A, no partner.
14. If #13 was no, what were the reasons he did not attend?
- a. He was working during my PMTCT appointments \_\_\_\_\_ Yes / No
  - b. He lives or works far away \_\_\_\_\_ Yes / No
  - c. He felt unwelcomed/uncomfortable at the clinic \_\_\_\_\_ Yes / No
  - d. I did not want him to attend \_\_\_\_\_ Yes / No
  - e. He did not want to attend \_\_\_\_\_ Yes / No
  - f. He had other responsibilities \_\_\_\_\_
  - g. Other, please specify \_\_\_\_\_
15. Did your male partner provide support for your child's delivery? Please select the most accurate answer.
- a. I do not have a male partner
  - b. No, my male partner did not provide any type of support for my child's delivery.
  - c. My male partner provided funding for me to get to the hospital, but did not come himself.
  - d. My male partner escorted me to the hospital while I was in labor.
  - e. My male partner visited me in the hospital after my child was born.

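### Delivery-survey items 13 and 15 on partner support are bounded by the woman's own PMTCT visits and by hospital birth, both parts of complete PMTCT, and item 15 cannot record support at a birth elsewhere

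*Combined protocol and SAP*

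**What the plan says.** **Item 15.** The English delivery survey (Appendix IIB, Partner Support) offers no partner, no support, or four positive options. The first positive option is "c. My male partner provided funding for me to get to the hospital, but did not come himself". The Swahili form (Kiambatisho IIB) matches it: "c. Mpenzi wangu alinipa alinifadhili ili nifike hospitali, lakini hakuja", then "d. Mpenzi wangu alinindikiza hadi hospitali nilipokuwa na maumivu ya kujifungua" (he escorted her to the hospital in labour) and "e. Mpenzi wangu alinitembelea hospitali baada ya kujifungua" (he visited her in hospital afterwards). The last option combines escorting and visiting. A woman with a partner otherwise has only "b. Hapana, mpenzi wangu hakutoa usaidizi wowote kwa wakati wa kujifungua kwangu" (no support of any kind). There is no free-text option. The Luo form has the same structure.

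**Item 1** of the same form records births at home, with a traditional attendant or elsewhere. Nothing routes these women past item 15.

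**Item 13** asks how many PMTCT appointments the partner attended with her (none, 1, 2, 3 or more). It does not ask how many she attended.

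**Outcome and intervention.** Table 6 lists "Hospital-based delivery" and attending antenatal appointments on time among the services that make up complete PMTCT, and missing any one service scores 0. The intervention summary in section 1 says the SMS messages support both behaviours.

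**Use of partner support.** The Objective 1 model adjusts for "selected covariates (e.g., age, partner support, depression" and others. The same paragraph plans to examine change in partner support at delivery and at six months. The paragraph on participant surveys says that changes in the repeated measures may mediate or moderate the effect. Table 1 lists "Male partner support" among the outcomes targeted by version 2.1. No section says which items form the partner-support variable, how it is scored, or which time point supplies the covariate.

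**The concern.** Two of the delivery-survey items that an analyst could use as partner support can only be positive, or can only be high, when the woman has had the hospital or clinic contact that the primary outcome also counts.

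This can mislead in two ways. First, recorded support would be associated with complete PMTCT even if partners made no difference, because women who gave birth outside hospital are pushed into the no-support category and also score 0 on the outcome. Second, if HITSystem 2.1 raises hospital delivery or attendance, recorded support rises in that arm with partners unchanged. That rise could be reported as an improvement in a targeted outcome, or as a pathway by which the intervention works. Separately, support given at a home birth is misclassified whatever analysis is done.

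**Working it through.** The plan gives no figure to reproduce here. The core is a reading check. The arithmetic only illustrates size.

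**1. Reading check.** Positive options in item 15 that do not mention a hospital: 0 of 4, in all three languages. Item 12 (support in pregnancy) has nine rows, 12b to 12j. Seven of them (12c, 12d, 12f to 12j) need neither a visit nor a hospital birth; 12b and 12e refer to travel to hospital and to PMTCT visits. The enrolment survey asks about the partner attending PMTCT visits (21a, 22a) and attending the delivery (21i, 22i). Item 12 has no row for either, so items 13 and 15 are their only counterparts after birth.

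**2. Spurious association of item 15 with complete PMTCT.** Let h be the share of hospital births, s the share truly supported (independent of birthplace and outcome), and c overall completion. Recorded support is true support at a hospital birth. Completion requires a hospital birth. Then:

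- completion if recorded as supported = c/h
- completion if recorded as unsupported = c(1 − s)/(1 − sh)

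Take c = 0.12. This is the pilot rate of guideline-adherent viral load testing (50/424, Table 3), not of complete PMTCT, but Table 4 uses 0.12 as one standard-of-care rate of complete PMTCT. The values of h and s are assumptions, as the documents give neither. With s = 0.6:

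| h | Recorded supported | Recorded unsupported | Odds ratio |
|---|---|---|---|
| 0.95 | 0.126 | 0.112 | 1.15 |
| 0.90 | 0.133 | 0.104 | 1.32 |
| 0.80 | 0.150 | 0.092 | 1.74 |
| 0.70 | 0.171 | 0.083 | 2.29 |
| 0.60 | 0.200 | 0.075 | 3.08 |

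Example at h = 0.70: 0.12/0.70 = 0.171; 0.12 × 0.4/(1 − 0.42) = 0.083; odds 0.207 and 0.090; ratio 2.29. Varying s at h = 0.70, the unsupported rate is 0.072/0.72 = 0.100 for s = 0.4 (odds ratio 1.86) and 0.024/0.44 = 0.055 for s = 0.8 (odds ratio 3.59).

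**3. Spurious arm difference on item 15.** With the same true support in both arms, the difference is s(h1 − h0). For hospital births of 90% vs 95%, 80% vs 90%, 70% vs 85% and 60% vs 80% (standard of care vs HITSystem) and s = 0.6, recorded support differs by 3, 6, 9 and 12 percentage points. For s from 0.4 to 0.8 the range is 2 to 16 points.

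**4. Item 13.** If a partner attends each visit independently with probability p, the chance he attended any of v visits is 1 − (1 − p)^v. Moving v from 3 to 4 (assumed) gives:

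- p = 0.1: 1 − 0.9³ = 27.1% to 1 − 0.9⁴ = 34.4%
- p = 0.3: 1 − 0.7³ = 65.7% to 1 − 0.7⁴ = 76.0%
- p = 0.5: 1 − 0.5³ = 87.5% to 1 − 0.5⁴ = 93.8%

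**5. Effect on the arm comparison.** Take completion of 12% vs 32% (Table 3's anticipated rates). The unadjusted odds ratio is (0.32/0.68)/(0.12/0.88) = 3.45. Fitting a logistic model to the expected cell probabilities, with recorded item 15 support as covariate, s = 0.6 and no site clustering, gives adjusted arm odds ratios of 3.44, 3.40, 3.32 and 3.22 in the four scenarios of step 3.

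**The case against.** The best case for the plan is that nothing in it commits the analysis to items 13 or 15. Several parts of that case stand.

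- A reader might infer that partner support as a whole is tied by construction to the primary outcome. The documents do not support this. Most of item 12 is free of hospital contact, and the enrolment items come before delivery and cannot depend on place of birth.
- A reader might also infer that the primary treatment comparison is materially biased. An enrolment covariate is a natural reading of the Objective 1 model, and even the worst scenario above moves the arm odds ratio only to 3.22.
- The mediators set out for Objective 1 are information or knowledge and motivation. Partner support as a mediator rests on the looser statement about survey changes, and the moderator and change analyses are post hoc.
- Neither item is asked at enrolment or six months in the same form. Enrolment asks about importance and expectation, and the six-month item 9a concerns the child's appointments. A change score from them would be hard to build, so a comparison of arms at delivery is the more likely use.
- The link between item 15 and hospital birth is usual rather than absolute. A woman could give birth on the way, or be admitted and visited afterwards.
- That HITSystem raises uptake is a hypothesis, and the rates used above are assumed.

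Two arguments do not remove the point. Item 1 shows where the birth took place, but it cannot recover whether a partner helped at a home birth. And although asking about hospital-related support fits the programme's aims, both items sit under the Partner Support heading and are the only follow-up to the enrolment questions on attending visits and the delivery. An analyst could reasonably include them.

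**Conclusion.** The point holds for items 13 and 15 only. Item 15 misclassifies support at non-hospital births in all three languages, and item 13 is capped by the woman's own attendance. Both limits coincide with components of complete PMTCT and with behaviours HITSystem 2.1 targets.

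The consequence is conditional. If either item enters a partner-support predictor, mediator or change outcome, it can produce a false association or a false arm difference. For item 15, with 60% true support, the odds ratio is 1.15 to 3.08 for hospital births of 95% down to 60%. The arm difference is 2 to 16 points across the scenarios. These sizes depend on hospital-birth and support rates that the documents do not give, and on true support being unrelated to birthplace and outcome. The primary arm effect is barely touched. This is a cheap improvement to a secondary measure, not a threat to the trial's main result.

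**What to change.** 1. For delivery surveys still to be done, add an option to item 15 in English, Swahili and Luo for support at a birth outside a hospital, and record the form version. The sample-size text for Objective 2 describes ten sites still enrolling and seeks 300 more women, so this may still be possible.
2. State in the analysis plan which items form the partner-support score and at which time point. Keep items 13 and 15 out of any such score used as covariate, moderator or mediator for complete PMTCT or hospital delivery.
3. Take any partner-support covariate in the primary model from the enrolment survey only. Delivery-survey item 12 is not a substitute: it is measured after randomisation, and partner support is itself a HITSystem 2.1 target.
4. For forms already completed, report item 15 descriptively by place of birth (item 1). Do not read a comparison of arms among facility births alone as causal, because it conditions on an outcome the intervention aims to change.
5. Report item 13 relative to the number of visits she attended, taken from HITSystem or clinic records. The open top category (3 or more) makes this approximate.

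Cost: one response option translated into two languages, two form versions in the data, a few sentences in the plan, and a slightly shorter delivery partner-support score. The enrolment covariate measures expectation and importance rather than support received, and should be described that way.
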